## 6.8 Packing and Labeling

The trial medication will be packed by Roche Pharma AG.

One vial of 40 mL concentrate contains 1,000 mg obinutuzumab, corresponding to a concentration before dilution of 25 mg/mL.

The trial medication will be provided free of charge by Roche Pharma AG (Roche Pharma AG, [name]) and will be delivered to the trial site or the pharmacy of the trial site.

The trial medication will be labeled by Roche Pharma AG according to § 5 of GCP-V.

## 6.9 Delivery and Drug Accountability

The investigator will confirm correct receipt of the trial medication in writing and ensure that the medication is stored safely and correctly. The trial medication must be carefully stored in accordance with manufacturer's instructions at 2-8 °C and dry at the study sites in a locked area with restricted access, separately from other drugs, and kept out of the reach and sight of children. The investigator will document the distribution and return of the trial medication to the patient with the date, recording the quantity distributed and used on the forms provided for this purpose. The site monitor will periodically check the supplies of trial medication held by the investigator to ensure the correct accountability of all trial medication used. At the end of the trial, all unused trial medication and all medication containers will be completely returned to Roche Pharma AG. It will be assured that a final report of the drug accountability is prepared and maintained by the investigator.

The medication must not be used after the expiry date, which is stated on the carton after EXP. The expiry date refers to the last day of that month.

## 7 IRRADIATION

The CT for 3D treatment planning is scheduled for week 7 and should be done using appropriate positioning devices (e.g. thermoplastic masks etc.). The response to the first 4 Gazyvaro administrations is also assessed using this CT. The irradiation occurs in week 9 after der fifth Gazyvaro administration (week 8).

### 7.1 Target volume

A 3D treatment planning is mandatory. The target volume should be assigned as involved site according to the guidelines of the International Lymphoma Radiation Group (ILROG) [60]:

The clinical target volume (CTV) encompasses the original GTV (at study inclusion). Normal structures such as lungs, kidneys, and muscles that were clearly uninvolved, though previously displaced by the GTV, should be excluded from the CTV according to clinical judgment. Potential subclinical involvement should also be considered. Therefore, the CTV should also include at least adjacent lymph nodes in that site and a generous margin dictated by the clinical situation. If there are questions about the delineation of the target volume the trial center in Heidelberg should be contacted.

Although a LDRT with 2x2 Gy will be carried out initially, the treatment plan should be prepared for a dose of 40 Gy in 20 fractions and the usual normal tissue constraints should be accepted for this dose. If a salvage irradiation is necessary after the FDG-PET/CT in week 18, the same irradiation plan should be used.

## 7.2 LDRT (week 9)

The irradiation in week 9 is a LDRT using 2x2 Gy on two succeeding days (no start on a Friday or before a holiday). The dose delivery should be according ICRU50. The irradiation delivery may include photons, electrons and protons.

## 7.3 Salvage irradiation (week 20-23)

All patients with PET positive lymphoma before the first Gazyvaro administration (initial FDG-PET/CT), will get an additional FDG-PET/CT in week 18 which should be sent to the trial center in Heidelberg. All of those patients who do not show a morphologic CR/PR or do not have a metabolic CR will get a salvage irradiation starting in week 20.

The target volume is identical to the initial LDRT irradiation in week 9. The dose is 18 x 2 Gy (ICRU 50). The same positioning devices, the same planning CT and the same treatment plan as for the LDRT should be used (see above).

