**Background**

Large field radiation therapy has proven to be superior to more limited fields radiation in early stage follicular lymphoma in prolonging PFS (ARO 98-01 trial, personal communication [name])

The MIR trial showed, that at least in the short time follow-up, the addition of MabThera to a small-field radiation therapy in conventional dosage can lead to at least equal results concerning the PFS as compared to the historic large field data of the ARO 98-01 trial. However, the toxicity has been shown to be lower (Herfarth et al. 2014).

The metabolic CR rate as demonstrated by FDG-PET was identified as a prognostic marker for freedom of recurrence in advanced stage of follicular lymphoma (Trotman et al. 2011 PRIMA trial).

Immune modulating radiation therapy alone using a low-dose of 2 x 2 Gy (LDRT) has been shown to be effective in inducing CR in about 60% of follicular lymphoma in a prospective trial (Haas et al 2003) or 48% in the British FORT trial (Hoskin et al. 2014). It can be speculated that a CR-reponse to LDRT identifies specific subtypes of follicular lymphoma. Also, it is not known whether a combination of LDRT with anti-CD20 antibody therapy may enhance the CR-rate.

The goal of the current trial is a further reduction of the radiation dose in patients with a good response to a combination of LDRT and anti-CD20 immunotherapy. The shift from MabThera to Gazyvaro might lead to an even more effective treatment, which can be proven by the morphological response in week 7 and the MRD eradication in comparison to the MIR trial. Patients with insufficient response (no metabolic CR) after LDRT will receive an additional radiation dose of 36 Gy adding up to the total dose 40 Gy of the MIR trial.

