### Radiation therapy

- Involved site radiotherapy of the involved lymph node regions: 2 x 2 Gy in week 9 on two consecutive days (after 5th administration of Gazyvaro)
- Salvage radiotherapy if there is no metabolic CR **and** morphological PR/CR at week 18: additional 18 x 2 Gy (5x2 Gy/week) starting from week 20 (without Gazyvaro)

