## STUDY FLOW CHART

Two stage Screening:

- Histology and CT or MRI: centrally approved follicular lymphoma grade 1/2 in clinical stage I/II (max. 93 patients)
- FDG-PET/CT: exclusion of stage III/IV patients (approx. 15%= 14 patients)  
Inclusion of max 79 patients: ca. 70% (=55 patients with remaining lymphoma); approx. 30% (=24 patients with metabolic CR)  
Drop-out-rate: approx. 10% (analyzable for primary endpoint 50 patients with remaining PET positive lymphoma)

\* = centrally reviewed

PET-pos (PET+): PET positive residual lymphoma  
 PET-neg. (PET-): metabolic CR  
 W: week  
 FU: Follow-up examinations  
 morph. SD: morphological SD

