## SUMMARY

*Extended field* or total nodal irradiation had been the gold standard for early stage follicular lymphoma for a long time in Germany. An *involved field* (IF) irradiation has been favored due to the toxicity of large field irradiation in other countries (e.g. USA). However, smaller irradiation fields have been accompanied with an increased risk of recurrence [2, 3]. A combination of *involved field* irradiation with the anti-CD20 antibody Rituximab (MIR trial) has led to similar efficacy results compared to the large field irradiation but with markedly reduced side effects [4].

Haas et al. showed in a prospective trial, that a low dose radiation therapy (LDRT) can lead to a complete remission in up to 60% in follicular lymphoma [5]. This is presumed to result from immune modulatory effects induced by LDRT. The effectiveness of LDRT could also be demonstrated in another prospective, randomized British trial (FORT trial [6]: 2 x 2 Gy vs. 12 x 2 Gy) with a CR rate of 40% after 2 x 2 Gy (60% after 12 x 2 Gy). Currently, it is unknown, which patients need a higher radiation dose and which not.

A metabolic complete remission (CR) is an important prognostic marker for progression-free survival. According to the results of the PRIMA trial, CR is a very strong predictive parameter if the CR is established using FDG-PET [7].

In the present GAZAI trial, patients with early stage nodular follicular lymphoma will be treated in a combined approach of immunotherapy with an anti-CD20 antibody and small field (involved site) irradiation as in the MIR trial. In GAZAI, the fully humanized anti-CD20 antibody Obinutuzumab (GAZYVARO) will be used, which showed a high efficacy in combination with bendamustin in patients with follicular lymphoma refractory to Rituximab (GADOLIN trial) [8]. In addition, the radiation dose will be limited to 2 x 2 Gy in responding patients. A dose build-up to a total of 40 Gy (dose in the MIR trial) will be performed in case of failure to achieve a complete CR based on a FDG-PET in week 18.

Primary endpoint of the trial is the rate of CR (based on FDG-PET/CT) after Obinutuzumab and 2x2 Gy IS radiotherapy in week 18. Secondary endpoints are the morphological CR rate in week 7, week 18 and month 6, the PFS, the toxicity, the recurrence rate, the recurrence pattern, overall survival and quality of life.

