### Role of FDG-PET

The routine staging diagnostic procedures using CT/MRI will be augmented by a FDG-PET/CT examination in the GAZAI trial. The total radiation dose will then be defined response adapted by a second FDG-PET.

Since the sensitivity and specificity of FDG-PET is higher compared to sole morphological imaging, all patients will get an initial FDG-PET/CT. This has to be performed at least 5 weeks after a surgical procedure (e.g. lymph node sampling) for minimizing the risk of false positive results.

LDRT alone of the involved lymph nodes regions results in responses shown in Table 2. However, LDRT alone leads less often to a CR than a full dose radiation therapy in these patients (see Table 1 and 2 and the FORT trial).

Since a negative FDG-PET is an independent predictive factor regarding PFS [7, 51], the decision for or against salvage radiation will be done based on a restaging FDG-PET/CT (FDG-PET positive: salvage RT of additional 18 x 2 Gy; FDG-PET negative: no salvage RT).

Since only patients with initially PET positive lymph nodes are valuable for the evaluation of the primary endpoint (metabolic CR rate after LDRT and anti-CD20 antibody), the FDG-PET in week 18 can be omitted in case of FDG-PET negativity at the initial staging (e.g. all macroscopic pathological lymph nodes were surgically removed).

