### 3. TRIAL CONCEPT/ DESIGN

GAZAI is a prospective, open, nationally multi-center phase II trial for evaluation of LDRT in combination with Gazyvaro (Obinutuzumab) in patients with early stage nodal follicular lymphoma grade 1/2. Patients will get a completion of the “full” radiation dose in case of not reaching a sufficient response (metabolic CR *AND* morphologic PR/CR) after LDRT.

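### The protocol carries two different triggers for salvage irradiation, and they conflict for patients with metabolic CR but morphologic SD or PD at week 18

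*Combined protocol and SAP*

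**What the plan says.** The trigger for the additional 18 x 2 Gy appears in several places.

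- **Section 7.3 (treatment section):** "All of those patients who do not show a morphologic CR/PR or do not have a metabolic CR will get a salvage irradiation". Failing either criterion is enough.
- **Section 3 (design):** the full dose is completed "in case of not reaching a sufficient response (metabolic CR *AND* morphologic PR/CR) after LDRT". This is the same rule stated from the other side.
- **Section 1.2, Role of FDG-PET:** the decision rests on the restaging PET, with both branches given: "FDG-PET positive: salvage RT of additional 18 x 2 Gy; FDG-PET negative: no salvage RT". Morphology plays no part.
- **Synopsis, Background:** "Patients with insufficient response (no metabolic CR) after LDRT will receive an additional radiation dose of 36 Gy".
- **Summary:** the dose is built up "in case of failure to achieve a complete CR based on a FDG-PET in week 18".
- **Synopsis, Radiation therapy:** salvage applies if there is no metabolic CR, then a bold conjunction, then "morphological PR/CR at week 18: additional 18 x 2 Gy (5x2 Gy/week) starting from week 20". How far the negation reaches is unclear.
- **Study Schedule, footnote 6:** salvage follows a positive week-18 PET, and the stated exemption is metabolic CR together with morphologic PR. Metabolic CR with SD or PD is not mentioned.
- **Section 1.2 (Low dose radiation therapy) and section 1.3:** salvage follows failure to reach complete remission, without saying whether metabolic or morphologic.

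The Study Flow Chart legend gives "PET-neg. (PET-): metabolic CR" and also lists "morph. SD: morphological SD".

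**The concern.** A patient who is PET-negative at week 18 but whose nodes have not shrunk enough for a PR is to be irradiated according to sections 7.3 and 3, and is not to be irradiated according to section 1.2. Both are current text. The difference is 36 Gy, in a trial whose stated goal is to reduce dose according to response and whose benefit-risk argument in section 1.3 leans on the salvage step.

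The primary endpoint is safe: metabolic CR is read in week 18 and salvage starts in week 20. What follows is exposed:

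- Toxicity and month-6 morphologic response would depend on which wording was followed.
- Section 2.1 plans to report recurrence sites in the subgroup that is PET-negative at week 18. That subgroup could mix patients treated to 4 Gy and to 40 Gy without a rule explaining the mix.
- PFS is affected for SD patients. Morphologic PD is already a PFS event under section 11.6.
- Section 11.3 limits the per-protocol population to patients deviating less than 20% from the protocol-defined dose. If that dose includes radiation, membership cannot be determined for these patients.

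**Working it through.** **Dose at stake.** LDRT is 2 x 2 = 4 Gy and salvage is 18 x 2 = 36 Gy, so the total is 4 + 36 = 40 Gy. This reproduces the protocol's stated total.

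**Are both rules about the same patients?** Yes. Section 7.3 speaks of metabolic CR and section 1.2 of a negative PET; the flow chart legend makes these the same.

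**Enumeration.** Two metabolic states (CR, no CR) by four morphologic states (CR, PR, SD, PD) give 2 x 4 = 8 combinations. Each row below stands for two of them.

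| Metabolic | Morphologic | Sections 7.3 and 3 | Section 1.2, Role of FDG-PET |
|---|---|---|---|
| CR | CR or PR | no salvage | no salvage |
| CR | SD or PD | **salvage** | **no salvage** |
| no CR | CR or PR | salvage | salvage |
| no CR | SD or PD | salvage | salvage |

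Sections 7.3 and 3 give salvage in 6 of 8 combinations and section 1.2 in 4 of 8. They agree in 6 and disagree in 2.

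In the Synopsis radiotherapy line, if the negation covers the whole conjunction, the result is the section 7.3 rule. Read strictly word by word (no metabolic CR, but PR/CR present), it would give salvage in only 2 of 8 and match neither rule. That reading is unlikely to be intended; it shows only that the line cannot settle the question.

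**Per-protocol consequence, if dose includes radiation.** Omitting salvage where it was required is a shortfall of 36/40 = 90%. Giving it where it was not required is an excess of 36/4 = 900%. Either far exceeds 20%.

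**How many patients?** The documents give no rate of metabolic CR with SD or PD. Two illustrations, both resting on assumptions:

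- The plan expects 0.60 x 50 = 30 metabolic CRs. If 2% to 20% of these had SD or PD, that is 30 x 0.02 = 0.6 to 30 x 0.20 = 6 patients. Salvage would be given to 20/50 = 40% under the PET-only rule, against (20 + 0.6)/50 = 41% to (20 + 6)/50 = 52% under the two-criterion rule.
- Suppose total response after 2 x 2 Gy alone carried over: 80% to 95% in Table 2, and 74% in the first FORT figures in section 1.1.2. Then SD or PD would occur in 50 x (1 - 0.95) = 2.5 to 50 x (1 - 0.80) = 10 patients, or 50 x (1 - 0.74) = 13. Only those who were also PET-negative would be affected. Those cohorts had no obinutuzumab and different timing, so 13 is a rough ceiling, and the true number may be zero.

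**The case against.** The best counter-argument is that section 7.3 is the operative text and section 1.2 is rationale. The Synopsis Background and the Summary say when salvage is given, not that it is withheld after metabolic CR, and may be shorthand. On that view one explanatory sentence stands against the treatment section, which an investigator would follow. This lowers the weight of the conflict but does not remove it: section 1.2 states the no-salvage branch outright, no text gives section 7.3 precedence, and footnote 6 of the Study Schedule, a working page for sites, also starts from a positive PET. It is fair that footnote 6 also omits metabolic CR with morphologic CR, so it is not an exhaustive rule.

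The PD case is weaker than the SD case. Section 5.5.1 lists progression as a possible reason for withdrawal, and section 8.3 puts new lymphoma lesions in PET score 5, so PD through a new lesion would often not coexist with metabolic CR. That stands. The SD case is untouched by it.

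Week-18 PETs go to the trial center for review, which may limit divergence between sites. Section 14.2, however, covers reading the images and does not say which rule then applies.

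The flow chart itself is not visible in the text reviewed. Its legend mentions morphologic SD, so it probably addresses this case. Whatever it shows, sections 1.2 and 7.3 remain opposed.

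**Conclusion.** The contradiction is real and must be corrected. It covers 2 of the 8 week-18 response combinations, most firmly metabolic CR with morphologic SD, and means 4 Gy or 40 Gy for each patient concerned. This follows from the wording alone and needs no assumption about rates. The number of patients is unknown, and the illustrations above carry no weight in the conclusion. The need for correction rests on conflicting treatment instructions, not on an expected effect on the main result, which is unchanged.

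**What to change.** State one salvage criterion and repeat it in identical wording in the Synopsis (Background and Radiation therapy), footnote 6 of the Study Schedule, the Summary, section 1.2 (Low dose radiation therapy and Role of FDG-PET), section 1.3, section 3 and section 7.3. The wording should say explicitly whether metabolic response, morphologic response or both decide, and should resolve all 8 combinations. Check the flow chart against it. Which rule is right is for the sponsor to settle.

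Optional, and only if the reconciled rule uses morphology as well as PET: tabulate week-18 metabolic by morphologic response, and report recurrence in the subgroup PET-negative at week 18 separately by salvage given or not given. Week-18 morphologic response is already a secondary endpoint, so no new data are needed, but the cells would be small.

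The cost is protocol wording only. The primary endpoint and sample size stay as they are.

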# 8. METHODS OF DATA COLLECTION / STUDY VISITS

## 8.1 Initial Staging

The extent of the lymphoma manifestation will be assessed according the Ann-Arbor classification system and using 3D imaging and bone marrow aspiration. A pathological staging is not necessary.

### 8.1.1 Procedures

Medical history (incl. of B-symptoms)
Current medication
Clinical examination (including palpation of lymph node regions)
Shipping of the biopsy tissue to a reference pathologist of the GLSG
Laboratory testing:
- Differential blood cell count (hemoglobin, leucocytes, thrombocytes, neutrophils, lymphocytes)
- Clinical chemistry (sodium, potassium, AST/ALT, total bilirubin, alkaline phosphatase, creatinine)
- LDH
- albumin, immunoglobulins, immunefixation
- $\beta_2$ microglobuline
- Peripheral blood (10 ml EDTA) for MRD analysis and STRECK tube (10 ml) for cell-free DNA collection
- Hepatitis- und HIV – serology (not applicable if there are values < 3 months )
- Pregnancy test (serum) for all women with childbearing potential (including tubal ligation)
CT or MRI (<= 4 months), if necessary: additional ultrasound
- head&neck*
- thorax*
- abdomen*
- pelvis including inguinal region*

\*These regions must be screened using 3D sectional imaging and should also be scanned during the follow-up examinations from months 6 on. Ultrasound can be used additionally, but it cannot replace a CT or MRI since the morphological remission criteria are based on 3D sectional imaging. A FDG-PET/CT of these regions can be used instead of CT or MRI.

Site-specific examinations:

Thyroid testing in case of cervical or supraclavicular lymphoma (TSH, fT3/fT4)
Consultation of a head&neck in case of supra-diaphragmal lymphoma

8.1.2 Risk profile and FLIPI

A risk profile according to the "Follicular lymphoma International Prognostic Index (FLIPI)" [61] and additional potential risk factors should be recorded.

General condition ECOG 0, 1 or 2
Age $\leq$ 40, 41 - 60, $>$ 60 years
Largest lymphoma $<$ 3 cm or $\geq$ 3 cm in max. diameter (sectional imaging)
Morphologically macroscopic tumor remaining after surgical intervention for proof of histology stage I or II
Serum-LDH normal or elevated
Serum- $\beta_2$ microglobulin ( $\beta_2m$ ) normal or elevated
Hemoglobin $\geq$ or $<$ 12 g/dl

The actual concomitant medication should be checked at each visit and should be documented in the patient chart and the CRF.

8.1.3 Examinations after inclusion and before start of therapy

FDG-PET/CT incl. central review (not applicable if already done for initial staging (see above))
EORTC QLQ-C30 and FACT-Lym questionnaires

8.1.4 Examinations during therapy (up to week 18)– **before each Gazyvaro administration:**

Differential blood cell count (hemoglobin, leucocytes, thrombocytes, neutrophils, lymphocytes)
Assessment of AEs
Pregnancy test (serum or urine) in premenopausal female patients before Gazyvaro administration in week 1, week 4, week 8, week 12 and week 16. In case of a positive urine pregnancy test, dosing will be delayed, until patient's status is determined by a serum pregnancy test

– **week 7:**

CT imaging of the involved lymphoma region for radiation planning and response assessment
Palpation of the lymphatic region
Laboratory testing:
- Differential blood cell count (hemoglobin, leucocytes, thrombocytes, neutrophils, lymphocytes)
- clinical chemistry (sodium, potassium, AST/ALT, total bilirubin, alkaline phosphatase, creatinine)

- LDH
Assessment of AEs

- week 18

Medical history
Clinical examination (including palpation of lymph node regions, skin reaction in the radiation area)
ECOG-Performance status
Laboratory testing:
- Differential blood cell count (hemoglobin, leucocytes, thrombocytes, neutrophils, lymphocytes)
- clinical chemistry (sodium, potassium, AST/ALT, total bilirubin, alkaline phosphatase, creatinine)
- LDH
EORTC QLQ-C30, FACT-Lym questionnaires
In dependence of the initial FDG-PET/CT before the first Gazyvaro administration: 
 
• FDG-PET/CT of the initially involved region for response evaluation (central review) for patients with initially PET positive remaining lymphoma
 
• Contrast enhanced CT/MRI for patients with initially PET negative remaining lymphoma
 
• No imaging for patients without initially remaining macroscopic lymphoma after surgical intervention for proof of histology
 

Peripheral blood (10 ml EDTA) for MRD analysis and STRECK tube (10 ml) for cell-free DNA collection
Assessment of AEs

8.1.5 Follow-up examinations month 6, 12, 18, 24

Medical history (incl. assessment of B-symptoms)
Clinical examination (including palpation of lymph node regions, skin reaction in the radiation area)
ECOG-Performance status
Laboratory testing:
- Differential blood cell count (hemoglobin, leucocytes, thrombocytes, neutrophils, lymphocytes)
- Clinical chemistry (sodium, potassium, calcium, AST/ALT, total bilirubin, alkaline phosphatase, creatinine)
- LDH
- Total protein, protein-electrophoresis
CT or MRI (<= 4 months), if necessary: additional ultrasound
- head&neck
- thorax
- abdomen
- pelvis including inguinal region
Peripheral blood (10 ml EDTA) for MRD analysis and STRECK tube (10 ml) for cell-free DNA collection
EORTC QLQ-C30 und FACT –Lym questionnaires ( only month 12, 24 )
Assessment of AEs

**Independent of the follow-up examinations:** Pregnancy test (serum or urine) in all women with childbearing potential (including tubal ligation) if menstruation is overdue more than 2 weeks up to month 24

